Off note that the reported "normal range" of central blood pressure is estimated invasively while the participants are monitored in a controlled environment and under the effect of mild sedation. To prevent any harm to our study participants, we will take a holistic approach to risk stratify our patients while instigating treatment based on central or brachial pressures in order to avoid symptomatic hypotension along with drug side effects. The risk profiling will include age of the participants, aortic pulse wave velocity, baseline BP, degree of HTN induced end organ injury, BP response to exercise and central or brachial pressure indices including pulse pressure.

In case if patient has presenting BP characterised as grade II or higher HTN, a graduated approach will be adapted to lower the BP gradually by keeping an eye on the side effects of anti-HTN treatment.

CASP normal range						
Age (years)	Average (mmHg)	Minimum (mmHg)	Maximum (mmHg)			
20-30	101	90	112			
30-40	105	94	116			
40-50	108	97	119			
50-60	112	101	123			
60-70	115	104	126			
70-80	119	108	130			
80-90	122	111	133			

Table-1. Central Arterial Systolic Pressure (CASP) normal range as per age.

All AF patients will be assessed at baseline visits and at clinical follow-ups at RAH and Cardiovascular Centre, Norwood (Prof. [name]' rooms). Follow-up visits will be performed 3 monthly for the intervention group and six monthly for control as per treating electrophysiologist for 18-20 months (Tables 2 and 3). Participants will be risk stratified as per their central or brachial blood pressure indices into interventional and control group respectively.

The study will be approved by the ethics committee of RAH, University of Adelaide. Central blood pressure indices and carotid-femoral PWV analysis will be performed as per IMPULSE-AF validation study protocol. (CALHN Ethics and Research Committee Approval: R2010712, HREC Reference: HREC/16/RAH/269).

Table-2. Follow up and Investigations time line for Intervention Group (AFSS= AF symptom scale, CBP= central blood pressure, CPI= central pressure indices, EST= exercise stress test, PWV= pulse wave velocity, RFTs= Renal function test)								
0 months	3 months	6months	9months	12 months	15months	18-20 months		

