Demographics and cardiovascular (CV) risk profiling	CPI and PWV including lying and standing CBP	CPI and PWV including lying and standing CBP	CPI and PWV including lying and standing CBP	CPI and PWV including lying and standing CBP	CPI and PWV including lying and standing CBP	CPI and PWV including lyin and standing CBP		
*CPI and PWV including lying and standing CBP (Sphygmocor)	AFSS, RFTS	AFSS, RFTS	AFSS, RFTs	AFSS, RFTs	AFSS, RFTs	AFSS, RFTs		
Echo, EST, Holter 4-7 days, AFSS, Retinal examination, Serum and urinary analysis.	Holter 4-7 days	Holter 4-7 days	Echo, EST, Holter 4-7 days, Serum and urine analysis	Holter 4-7 days, Retinal examination	Holter 4-7 days	Echo, EST, Holter 4-7 day Retinal examination, Serum and uri analysis		

Tables to illustrate follow up and intervention time lines for two groups

*Offer treatment as per central BP targets. (Table-1).

Additional electro-anatomical mapping to estimate scar burden along with CMRI will be offered to patients listed for AF ablation. The CMR will be repeated after 12 months to assess AAD in a year as per IMPULSE AF protocol (CALHN Ethics and Research Committee Approval R2010712, HREC Reference: HREC/16/RAH/269)

Table-3. Follow up and Investigations time line for Control Group (AFSS= AF symptom scale, BBP= Brachial blood pressure, CBP= central blood pressure, CPI= central pressure indices, EST= exercise stress test, PWV= pulse wave velocity, RFTs= Renal function test)							
0 months	6months	11-13 months	18-20 months				
Demographics and cardiovascular risk profiling	BBP treatment targets as per current guidelines	BBP treatment targets as per current guidelines	BBP treatment targets as per current guidelines				
CPI, PWV (Sphygmocor) Brachial blood pressure (BBP) including lying and standing assessment, Retinal examination	Review for standard CV risk factor modification including AF and anti HTN treatment	Review for standard CV risk factor modification including AF and anti HTN treatment	Review for standard CV risk factor modification including AF and anti HTN treatment				

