Echo, EST, Holter 4-7 days, AFSS, Serum and urine analysis. Conventional cardiovascular risk factor (CVRF) management as per treating physician	Holter 4-7 days, AFSS, Conventional CVRF management as per treating physician	Echo, EST, Holter 4-7 days, AFSS, Retinal examination, Serum and urine analysis. CVRF management as per treating Physician	Echo, EST, Holter 4-7 days, AFSS, Retinal examination, Serum and urine analysis. CVRF management as per treating Physician				

Additional electro-anatomical mapping to estimate scar burden along with CMRI will be offered to patients listed for AF ablation. The CMR will be repeated after 12 months to assess AAD in a year as per IMPULSE AF protocol (CALHN Ethics and Research Committee Approval R2010712)

Following assessments are standard for AF care and will be offered to all (control and intervention) participants.

a) Baseline Assessment

At baseline, following assessment will be performed for all participants:

- Weight and height recorded to calculate BMI.
- Demographics and conventional cardiovascular risk factors profiling by recording fasting glucose, lipid profile, age, gender, smoking history, systolic, diastolic, and pulse pressure.
- Brachial and aortic blood pressure (BP) assessment in a supine position after a resting period of 10 min by a mercury sphygmomanometer. Sphygmocor device will be applied to the right forearm over brachial artery to determine the central blood pressure indices as described previously (IMPULSE-AF protocol). Brachial blood pressure will be assessed by recording phase I and V of Korotkoff sounds to determine the brachial systolic and diastolic BP, respectively.
- Conventional 12-lead resting electrocardiograms (ECG) will be recorded and interpreted according to the Minnesota code (Mc).

Protocol for HIGH IMPACT- AF study

Centre For Heart Rhythm Disorders, Royal Adelaide Hospital, University of Adelaide

- Exercise stress test as per Bruce Protocol to assess exercise capacity.
- Blood will be drawn following a 12-hour fast to determine plasma lipids, fasting glucose, hs CRP and renal function.
- Trans-thoracic Echo (TTE) will be performed to assess Biventricular systolic and diastolic function along with left atrial size.
- 4 to 7days Holter monitoring to evaluate AF recurrence and arrhythmia burden

b) Exercise Tolerance Assessment

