Exercise tolerance assessment as a part of AF management will be determined by Bruce protocol with gradual increase in treadmill gradient and velocity every 3 mins to achieve maximal target heart rate as per age by the following formula [220-Age for males, 220-Age x0.8 for females]. Where necessary, the test will be tailored as per individual age and effort tolerance with a view to assess the maximum workload performance with in period of 8-12 minutes. An experience doctor or an exercise physiologist will supervise the test. Continuous monitoring of 12 leads ECG and blood pressure will be performed. Data will be recorded continuously and stored digitally for analysis later on by an experienced exercise physiologist. Central pulse wave morphology and velocity will be determined pre and post exercise (+5minutes) by Sphygmocor device.

c) Holter Recording

4- 7 days Holter recordings will be obtained to determine recurrence of AF along with its burden. Briefly, a 3-lead electrocardiogram is recorded continuously by way of five electrodes positioned on the upper torso. Upon completion of the recording period, data will be imported into MediLog Darwin analysis software and automatically analysed by using R-wave detection.

E. STUDY INTERVENTIONS IN ADDITION TO STANDARD OF CARE IN AF PATIENTS

a) Non-invasive central blood pressure assessment

Non-invasive evaluation of central blood pressure indices and carotid-femoral PWV analysis will be performed as per IMPULSE-AF validation study protocol (CALHN Ethics and Research Committee Approval: R2010712, HREC Reference: HREC/16/RAH/269)

Non-invasive central blood pressure assessment will be performed at baseline, and at follow-up using the SphygmoCor applanation tonometry device (Fig 1). Central blood pressure indices, including central systolic, diastolic and pulse pressures with augmentation index will be recorded. Carotid-femoral pulse wave velocity (PWV) will be performed by applanation tonometry as per IMPULSE AF study protocol. The test is painless and typically takes10-15 minutes. In control patients, central blood pressure measurement will be performed as a single clinical assessment during their first visit after randomisation.

b) Atrial Fibrillation Severity Scale (AFSS)

Atrial Fibrillation Severity Scale (AFSS) will be used to quantify AF symptomatic burden. The AFSS is a validated scale with range of 3.25 [single

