Retinal photographs will be acquired from AF patients at baseline and during their follow up appointments yearly. Retinal vascular calibre will be measured from photographs using a validated computer program[22]. Retinal arteriolar and retinal venular calibre equivalents will be measured, and correlated with changes in central or peripheral blood pressures[22]. The acquisition of retinal image takes couple of minutes and it is a painless procedure that does not require any specific preparation.

[figure not shown]

Fig. 1. Sphygmocor applanation tonometry device (http://atcormedical.com/sphygmocor.html)

F. OUTCOMES OF THE STUDY

Primary outcomes to be evaluated include:

Association and Impact of central blood pressure control on AF outcomes (recurrence and AF burden).

Secondary Outcomes:

- Prevalence of central high blood pressure and aortic stiffness in AF patients with normal brachial BP.
- Association of brachial and central blood pressure indices including aortic stiffness to end organ insult and electro-anatomical remodeling of atria in AF patients.
- Correlating central blood pressure treatment target goals to proportionate decrease in events [Nephropathy (20% increase in ACR or 15-20% drop in estimated glomerular filtration rate (eGFR)), Left ventricular hypertrophy (LVH)/mass, LV diastolic dysfunction. Left atrial area and conduit vascular remodeling.
- Defining exaggerated BP response to exercise and postural change in our AF cohort and relating it with outcomes.
- > Number of anti-HTN required to achieve BP targets.
- Adverse events secondary to anti-HTN drugs including symptomatic postural BP drop of >20mmHg, acute kidney injury and electrolytes imbalance requiring hospitalization.

G. ETHICAL CONSIDERATIONS

Clinical Equipoise

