The study is a low risk, single blinded randomised trial to evaluate the impact and treatment of central high blood pressure on AF and CV outcomes. Central high blood pressure will be estimated by validated cuff based device (Sphygmocor) non-invasively. Vascular remodelling secondary to HTN, leads to aortic stiffness, which is a modifiable risk factor. At present, it is known that various anti-hypertensive agents can have significantly different effects on central aortic pressures despite similar brachial blood pressure valuation [23]. Agents such as inhibitors of the renin-angiotensin system and amlodipine could be started in individuals with increased aortic stiffness. As such, the investigators regarding the conduct of this study identify no specific ethical concerns.

Informed Consent

All patient participants will undergo a formal process of informed consent prior to study participation. Patients will be blinded with regard to their randomised group and will be treated for peripheral or central high blood pressure accordingly.

Drugs

No additional pharmaceuticals will be administered for the study protocol, with the exception of anti-HTN to achieve treatment target goals re central or brachial blood pressure. Side effects of anti HTN medication will be recorded by conventional clinical approach of reviewing the symptoms, documentation of postural drop in BP and monitoring of renal function tests during follow up or as required clinically.

Specific Safety Consideration

No significant increase in radiation dose is anticipated for the acquisition of electrophysiological data for the study because we are going to use 3D mapping to position the catheters in atria. The non-invasive assessment of blood pressure is not associated with any known risk. Retinal photography does not require any mydriatics.

H. ANALYSIS AND REPORTING OF RESULTS

Sample size calculation

Assuming the recurrence risk is 40% for AF in control, we estimate 90 patients in each group would give us 80% power to detect the 20% difference between groups at 5% significance level. Anticipating dropout rate of 28% over the course of the study, we would like to recruit 126 patients in each group.

Statistical Analysis

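### Six follow-up Holters in the intervention arm against three in control bias the AF recurrence comparison against treatment

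*Protocol*

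**What the plan says.** Section D sets the visit frequency by arm: "Follow-up visits will be performed 3 monthly for the intervention group and six monthly for control as per treating electrophysiologist for 18-20 months".

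The schedules carry this through to rhythm monitoring.

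- Table 2 (intervention) has a 4-7 day Holter in every post-baseline column: 3, 6, 9, 12, 15 and 18-20 months. The 12-month cell, for example, reads "Holter 4-7 days, Retinal examination".
- Table 3 (control) has one at 6, 11-13 and 18-20 months. The 6-month cell reads "Holter 4-7 days, AFSS, Conventional CVRF management as per treating physician".

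Both arms also have a baseline Holter. The Holter paragraph of Section D gives the purpose: "Holter recordings will be obtained to determine recurrence of AF along with its burden". No other method of detecting recurrence is named.

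Section F makes recurrence and burden the primary AF outcomes. It does not say which recordings count or over what window. Section H sizes the trial on recurrence alone: "Assuming the recurrence risk is 40% for AF in control, we estimate 90 patients in each group would give us 80% power" to detect a "20% difference between groups at 5% significance level".

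**The concern.** With intermittent monitoring, the chance that a patient is ever labelled recurrent grows with the number of recordings. Here that number differs by arm by design, so the observed recurrence rates are not comparable even if treatment has no effect. Randomisation and patient blinding do not help, because the imbalance is in the schedule itself. Time to first detection is affected too: AF can first be found at month 3 in the intervention arm and at month 6 in control.

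The direction is known for any such endpoint. More looking in the treated arm raises its apparent recurrence. A real benefit could be hidden, or a harm declared that does not exist.

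**Working it through.** **Monitoring by arm (Tables 2 and 3, after baseline)**

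- Intervention: 6 recordings, 6 × 4 = 24 to 6 × 7 = 42 days.
- Control: 3 recordings, 3 × 4 = 12 to 3 × 7 = 21 days.
- Ratio: 2.

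**The plan's own sample size (Section H)**

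Inputs: 40% versus 20%, two-sided 5% (sidedness is not stated; two-sided fits), 80% power. The pooled-variance formula gives

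n = [1.96·√(2·0.3·0.7) + 0.8416·√(0.4·0.6 + 0.2·0.8)]² / 0.2² = (1.270 + 0.532)² / 0.04 = 81.2, so 82 per arm.

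With continuity correction: (81.2/4)·[1 + √(1 + 4/(81.2·0.2))]² = 90.95, so 91. The stated 90 is therefore reproduced, to within one patient, as a continuity-corrected figure. By the uncorrected formula, 90 per arm gives 84% power. The figures below use the uncorrected formula throughout, so 84% is their reference.

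**Model for detection**

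Let q be the chance that one Holter shows AF. Assume that the planned rates (40% control, 20% treated) are what three Holters would detect, and ask what six would detect.

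*Independent recordings.* P(any AF in m) = 1 − (1 − q)^m.

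- No treatment effect: q = 1 − 0.6^(1/3) = 0.157, and six Holters give 1 − 0.6² = 64%.
- Planned effect: three Holters give 20%, so six give 1 − 0.8² = 36%.

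*Correlated recordings.* Beta-binomial with within-patient correlation ρ, a = q(1−ρ)/ρ and b = (1−q)(1−ρ)/ρ:

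P(any AF in m) = 1 − Π (b + j)/(a + b + j), for j = 0 to m − 1.

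Example at ρ = 0.5, where a + b = 1. Setting three Holters to 40% gives q = 0.251. Three are all negative with probability 0.749·1.749·2.749/6 = 0.600. Six are all negative with probability 0.600 × (3.749·4.749·5.749/120) = 0.600 × 0.853 = 0.512. Detected recurrence is therefore 49%.

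**Chance of a significant result, 90 per arm**

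Φ[(|d| − 1.96·SE₀)/SE₁], with pooled SE₀ and unpooled SE₁. For 64% versus 40%: SE₀ = √(0.52·0.48·2/90) = 0.0745 and SE₁ = √((0.24 + 0.2304)/90) = 0.0723. Then (0.24 − 0.146)/0.0723 = 1.30, which gives 90%.

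The protocol gives no ρ, so the whole range is shown. Control is 40% in every row.

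| ρ | Treated arm, no effect | Chance of false harm (nominal 2.5%) | Treated arm, true 20% | Power for planned effect |
|---|---|---|---|---|
| 0.9 | 42% | 4% | 21% | 79% |
| 0.8 | 44% | 7% | 22% | 73% |
| 0.6 | 47% | 16% | 24% | 61% |
| 0.5 | 49% | 22% | 26% | 54% |
| 0.4 | 51% | 31% | 27% | 46% |
| 0.2 | 56% | 56% | 30% | 28% |
| 0 | 64% | 90% | 36% | 8% |
| Common schedule, any ρ | 40% | 2.5% | 20% | 84% |

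**The case against.** The strongest reply is that the protocol never defines recurrence as AF on any scheduled Holter. A statistical analysis plan, not shown here, might use status at a fixed visit or only the shared visits, and the bias would then not arise. That is fair as far as the analysis goes. The unequal schedule, however, is fixed in this protocol, and the ordinary reading of a recurrence risk over follow-up is any detected recurrence.

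Other points stand in part.

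- **Burden.** Mean burden as a percentage of recorded time is largely unaffected by the number of recordings. The problem lies with the recurrence component, and with burden if it is summed over recordings.
- **Size.** Independent Holters are an extreme. Eligible patients include those with persistent AF, whose results should correlate strongly. At ρ = 0.9 the spurious excess is about 2 points. Direction is secure; size is not.
- **Power benchmark.** The stated 80% fits a continuity-corrected test, while the table uses an uncorrected one. The like-for-like reference is 84%, and every row with unequal schedules falls below it.
- **Recording length.** The 4-7 day range is the same in both arms, so it creates no planned imbalance.
- **Opposing bias.** More frequent contact in the intervention arm may improve care and favour treatment. That is a separate effect of unknown size, and it cannot be relied on to cancel this one.

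**Conclusion.** The concern holds. As written, the protocol looks for recurrence twice as often in the intervention arm, and any endpoint based on ever detecting AF, or on time to first detection, is biased against treatment. With no true effect, the spurious excess runs from about 2 points (ρ = 0.9) to 24 points (ρ = 0). For the planned effect, power runs from 79% down to 8%, against 84% on a common schedule. At a middle value of ρ = 0.5 the excess is about 9 points and power is 54%.

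These sizes rest on three assumptions: the planned 40% and 20% refer to three Holters, a beta-binomial model describes repeat recordings, and 90 patients per arm are evaluable. The direction needs only that some patients would be positive on an extra recording and negative on the three shared ones. Because the affected endpoint is the one the trial is sized on, this should be corrected before the arms are compared.

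**What to change.** In Section F, define primary recurrence as AF on any Holter at the time points common to both arms: 6 months, 12 months (11-13 in control) and 18-20 months. Use the same analysable recording length in both arms. Define burden as the percentage of analysable time in AF over those same recordings. State that the intervention-only Holters at 3, 9 and 15 months, and AF found only on them, are left out of the between-arm comparison and reported descriptively.

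This is a change of wording and leaves visits, treatment and sample size as they are. Its price is that three intervention-arm recordings per patient do not enter the primary comparison. It does not remove any difference in care that follows from the extra visits or from the treating team seeing the extra recordings. The same Holter schedule in both arms would also remove the detection imbalance. Matching control to the six-recording schedule would mean three further recordings per control patient, up to 3 × 126 = 378 in all.

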episode with minimal symptoms lasting for minutes] to 30 [continuous highly symptomatic episode lasting for 48 hours]. The scale also includes AF event frequency (scored 1-10), duration (scored 1.25-10) and global episode severity (scored 1-10). In addition, the AFSS assesses symptom severity via an associated symptom-specific continuous subscale (range, 0 [no symptoms] to 35 [severe symptoms]).

c) Serum and Urine Analysis

Venous blood samples (10ml) will be drawn from an antecubital vein after 10 minutes of supine rest and within five minutes following peak exercise to analyse atrial natriuretic peptide, serum markers of endothelial function (asymmetric dimethyl arginine, nitrate/nitrite), coagulation inflammation and fibrosis (C-reactive protein(CRP), tissue growth factor beta (TGF-B) and tumour necrosis factor (TNF)). Samples will be collected in appropriate tubes, centrifuged and plasma stored at -80°c. A preferably early morning urine sample will be collected to quantify albumin creatinine ratio (ACR).

- *d)* Recording of additional Electrophysiological (EP) parameters during AF ablation: Some of the study AF patients will be scheduled for pulmonary vein isolation (AF ablation) on clinical grounds at the Royal Adelaide Hospital. Conventionally, electro-anatomic mapping of the left atrium is performed by using the 3D mapping system during AF ablation. The following additional electrophysiological parameters will be recorded from the ablation catheter for these patients to characterise electro-anatomical atrial remodelling: effective refractory period, linear catheter conduction time, conduction velocity, proportion of fractionated electrograms, and bipolar voltage from the electroanatomic mapping system. This will add an extra 15mins to the procedure time without any additional requirements.
- *Non-contrast cardiac MRI (CMR) assessment of aortic distensibility.* In sub-group of 20-30 patients, scheduled for PVI (AF ablation) a non-contrast CMR will be performed to assess aortic distensibility (AAD) as per IMPULSE AF study Protocol (CALHN Ethics and Research Committee Approval: R2010712, HREC Reference: HREC/16/RAH/269). A repeat CMR will be performed to appraise (AAD) in a year's time.

f) Retinal photography and analysis

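### Ablation acts on the primary outcome, but randomisation names no stratification by ablation listing, and recurrence is read from intermittent Holters with no provision for ablated patients

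*Protocol*

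**What the plan says.** - **Ablation.** Section E(d) states: "Some of the study AF patients will be scheduled for pulmonary vein isolation (AF ablation) on clinical grounds at the Royal Adelaide Hospital". The notes under Tables 2 and 3 offer mapping and cardiac MRI to patients listed for ablation in both arms. Section E also says: "In sub-group of 20-30 patients, scheduled for PVI (AF ablation) a non-contrast CMR will be performed". Ablation is neither an exclusion nor a withdrawal criterion in Section C. Its timing and expected total number are not given.
- **Primary outcome.** Section F names AF recurrence and AF burden. Section D(c) says how they are measured: "4- 7 days Holter recordings will be obtained to determine recurrence of AF along with its burden". The baseline list in D(a) assigns Holter the same role.
- **Schedule.** Table 2 (intervention) has post-baseline Holters at 3, 6, 9, 12, 15 and 18-20 months. Table 3 (control) has them at 6, 11-13 and 18-20 months.
- **Randomisation and blinding.** Sections C and D describe randomisation to two arms and categorise patients by age and blood pressure status. No stratification factor is named, and ablation listing is not mentioned in connection with randomisation. Section G describes patients as blinded and does not say that clinicians are.
- **Sample size.** Section H takes 40% as the control recurrence risk and aims at a 20% difference with a 5% test. On that basis it says: "we estimate 90 patients in each group would give us 80% power".

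**The concern.** Ablation is a treatment for the condition that the primary outcome measures. Once a patient has been ablated, later Holters reflect the procedure as well as the blood pressure strategy. This can enter the comparison in two ways.

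First, patients listed for ablation at entry are likely to follow a different rhythm course from the rest. Without stratification, the arms may differ by chance in how many such patients they hold. In a trial of this size that imbalance need not be small.

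Second, AF may return between two Holters in a patient who was not listed. If that patient is then ablated and later Holters are clear, the recurrence is not seen. More such relapses in control would shrink a real difference, and more in the intervention arm would enlarge it. Recording frequency and review frequency differ between arms and referring clinicians are not described as blinded, so equal masking cannot be taken for granted. Burden and left atrial area, a secondary outcome, are exposed in the same way.

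**Working it through.** **1. The plan's own figure.** Inputs from Section H: 40% versus 20% (reading the difference as 20 percentage points), 80% power, 5% significance taken as two-sided.

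n = [1.96·√(2·0.30·0.70) + 0.842·√(0.40·0.60 + 0.20·0.80)]² / 0.20² = 81.2, so 82 per arm. With the continuity correction this becomes 91, against 90 stated. Dropout: 90/0.72 = 125, the figure in Section C; Section H gives 126. The sample-size arithmetic is sound. At 90 per arm, power is 84% uncorrected and 80% with the correction.

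**2. Holter coverage.** Intervention: 6 × 4-7 days = 24-42 days. Control: 3 × 4-7 days = 12-21 days. Over 18 months (about 548 days) that is roughly 4-8% and 2-4% of follow-up. A relapse between recordings is therefore possible in both arms.

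**3. Chance imbalance in listing.** With listed share s and 125 per arm under simple randomisation, the 95% range is ±1.96·√(2s(1−s)/125). The document gives no s, so a range is assumed:
- s = 10%: ±7.4 points
- s = 20%: ±9.9 points
- s = 30%: ±11.4 points

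The shift in the recurrence difference is the imbalance times the gap in recurrence risk between listed and unlisted patients. If that gap were 20 points (assumed), the shift at the edge of the range would be 0.074 × 20 = 1.5 to 0.114 × 20 = 2.3 points. If it were 40 points, it would be 3.0 to 4.6 points. The planned effect is 20 points.

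**4. Relapses hidden by ablation.** Let m be the share of recurrent patients who are ablated and then scored recurrence-free. The document gives no value, so m is purely an assumption. Observed risk = true risk × (1 − m). Power is at 90 per arm by the normal approximation without correction, with the corrected value in brackets.

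| m | Same in both arms | Control only |
|---|---|---|
| 0 | 40% v 20%, 84% (80%) | 40% v 20%, 84% (80%) |
| 10% | 36% v 18%, 78% (73%) | 36% v 20%, 67% (61%) |
| 20% | 32% v 16%, 71% (65%) | 32% v 20%, 45% (38%) |
| 30% | 28% v 14%, 64% (57%) | 28% v 20%, 24% (19%) |

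If the masking is in the intervention arm only, m = 20% turns 40% v 20% into 40% v 16%, a difference of 24 points. With no true effect (40% in both arms), m = 10, 20 or 30% in the intervention arm alone creates an apparent benefit of 4, 8 or 12 points. The chance of a significant result in that direction is then about 8, 20 or 40%, against a nominal 2.5%.

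In patients, m = 20% in control means 0.20 × 0.40 × 90 = about 7 people. In the intervention arm it means 0.20 × 0.20 × 90 = about 4.

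**The case against.** A reader might infer that patients will be ablated for relapse during follow-up and then scored recurrence-free. The documents do not establish this. They do not say when ablation happens. The MRI exclusion criterion for patients scheduled for ablation and the 12-month repeat scan both fit listing at or near entry. Nor do they say whether recurrence means AF on any post-baseline Holter or on the last one. If any Holter counts, a relapse recorded before ablation is kept. The pathway is possible because nothing rules it out, but it is not described.

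A reader might also take the 20-30 MRI patients (8-12% of 250) as support for a hidden share of 10-20%. They are a subgroup scheduled for ablation. They do not measure relapses missed by Holter and later ablated. The 40% control risk has no stated source either. If it was observed in a clinic where ablation is usual care, reducing it further counts the loss twice.

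Three further points carry weight:
- Listing at entry is a baseline factor, balanced in expectation by randomisation. Without stratification the cost is chance imbalance and lost precision, not systematic bias.
- Handling of post-randomisation ablation is commonly left to a SAP, and comparing strategies with ablation as background care is a legitimate estimand. The absence of an analysis rule is therefore not in itself an error.
- The severity scale (AFSS), taken at every Holter visit, scores event frequency and duration. It records symptomatic burden, however, and does not confirm rhythm.

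What these points leave standing is the protocol-level part. Stratification cannot be added by a later SAP, and the date and reason of each ablation are best captured prospectively.

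**Conclusion.** The point holds in a limited form. The protocol anticipates a procedure that acts on its primary outcome, names no stratification for it, and reads that outcome from sparse recordings that differ in number between arms.

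Chance imbalance in listing could reach about ±7 to ±11 points if 10-30% of patients are listed. Its effect on the 20-point comparison would be a few points under the gaps assumed above. Masking of relapses could cost power or bias the estimate either way, but the figures for it rest wholly on an assumed share. They show sensitivity and are not a forecast. Neither direction nor size can be derived from the document.

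It might also be inferred that ablation must count as a primary event, or that the main analysis should stop at ablation. The documents do not support either. Both are choices of estimand, and stopping at ablation conditions on a post-randomisation event. It would also often be unworkable for left atrial area: post-baseline echo is only at 9 and 18-20 months (intervention) or 11-13 and 18-20 months (control), so a patient ablated at 6 months has none before the procedure. The change is worth making because it is cheap and part of it cannot be made later.

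**What to change.** 1. Stratify randomisation by whether the patient is listed for AF ablation at entry (yes/no), and adjust the primary analysis for that factor.
2. Record the date and reason of every post-randomisation ablation, and report ablations by arm.
3. For patients not listed at entry, pre-specify an additional recurrence analysis that counts an ablation done for documented recurrent AF as a recurrence on its date. Present it alongside the Holter-only result.
4. Give burden and left atrial area restricted to pre-ablation recordings as a sensitivity analysis only.

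The cost is one stratification factor, two data items per ablation, one additional recurrence analysis and one sensitivity analysis. No procedure is added, and ablation decisions stay with the treating clinicians. The drawback is that the analysis in item 3 depends on referral by clinicians who are not described as blinded. If the arm reviewed more often is referred more often, it gains events. Persistent AF is eligible, so an ablation need not mean recurrence, which is why item 3 requires documented recurrent AF and stays secondary to the Holter result.
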